3.1 Control-IQ 1.5 Training Visit

225 After screening, participants will have a clinic visit at which they will undergo CGM and study pump
226 device training.

227 The device training visit should be completed within 2 weeks of screening, and may be performed the
228 same day as the screening visit. If not completed within 2 weeks of screening, re-review of screening
229 results by the investigator should be performed, who may ask for repeated testing as per investigator
230 judgement. The device training visit may be extended over the course of more than 1 session if needed.
231 The device training visit must occur in clinic and cannot be performed remotely.

232 A blood sample (venipuncture or fingerstick) will be obtained to send to the central laboratory for
233 HbA1c measurement.

234 A urine pregnancy test for all females who are premenopausal and not surgically sterile will be
235 completed.

236 Participants will receive supplies for blood glucose and ketone testing. Quality Control (QC) testing will
237 be performed on the meters before they are dispensed.

238 As all study participants are existing pump users (of any brand pump), pump settings will be transferred
239 over from the participant's current pump. The study investigator may then further adjust insulin delivery
240 profile settings as clinically indicated.

241

3.1.1 Training on System Use

242 All participants will receive study system training from a qualified trainer.

243 At a minimum training will include the following:

- 244 • Calibration of the CGM in accordance with manufacturer labeling
- 245 • Procedures for treating severe hypoglycemia
- 246 • Procedures for identifying potential infusion set failure and steps to take including the checking of the
247 blood ketone level and changing the infusion set

248 The participant will be given a User Guide as a reference as well as Hypoglycemia and Hyperglycemia
249 Treatment Guidelines as part of the Study Participant Instruction Sheet.

250 Participants will be instructed to download the study device prior to each phone contact or office visit.

251 The participant will be instructed to use the system in closed-loop mode except 1) when no calibrated
252 CGM sensor is available or 2) if insulin is delivered by any means other than the study pump (e.g.
253 injection of subcutaneous insulin via syringe in the event of infusion site failure). If insulin is delivered
254 by any means other than the study pump, participant will be instructed to turn off Control-IQ for
255 approximately four hours.

256 The participant will also be instructed to contact study staff during periods of illness with an elevated
257 temperature >101.5 degrees Fahrenheit (38.6 degrees Celsius), periods of significant illness, or during
258 periods of use of medications such as epinephrine for the emergency treatment of a severe allergic
259 reaction or asthma attack in addition to use of oral or injectable glucocorticoids to determine if closed-
260 loop use should be temporarily discontinued.

261 Participants taking SGLT-2 inhibitors will be instructed to discontinue use of their SGLT-2 inhibitor
262 during times of illness where they are at higher risk to develop ketones, to include temperature >101.5

263 degrees Fahrenheit (38.6 degrees Celsius), any gastrointestinal illness, dehydration, decreased PO intake,
264 fasting, or periods of significant illness.

265 Participants will be provided with contact information and will be asked to call the study clinical staff
266 for any health-related issues and for technical issues with the system. Participants may use the study
267 pump without Control-IQ activated and study CGM during periods of component disconnections or
268 technical difficulties.

269 Participants may use available manufacturer-provided CGM software and features of the study CGM
270 related to mobile data access or remote monitoring, but will be instructed not to use any third-party
271 components for this purpose. The t:connect mobile app from Tandem Diabetes Care will not be
272 available for use during the trial, and will not pair to the study pump.

273 Study staff will discuss with the participant that routine contact is required as per the study visit schedule
274 and will make arrangements with the participant for the contacts. If the participant cannot be reached, the
275 participant's other contact methods will be utilized, including the emergency contact. Participants who are
276 not compliant with the arranged contacts on two separate occasions may be discontinued at the discretion
277 of the investigator.

278 Participants will be instructed that they must have a care partner, trained in the study hypoglycemia and
279 hyperglycemia treatment guidelines, present during the study meal and exercise challenges, and present
280 overnight after the challenges. These hypoglycemia and hyperglycemia treatment guidelines will be
281 reviewed with the care partner prior to initiating any challenges.

282 Following the Control-IQ 1.5 Training Visit, participants will use the study pump for ~90 days during the
283 Treatment Period.

284 **3.1.2 Training on Management of Hypoglycemia**

285 The t:slim X2 with Control-IQ system will issue a predictive hypoglycemia alert (Control-IQ Low Alert)
286 when the system predicts BG <70 mg/dL within the next 15 minutes (<80 mg/dL when exercise mode is
287 activated). Participants will be permitted to change the CGM low glucose threshold alert setting on their
288 device or mobile app, but will be instructed to choose a value no less than 70 mg/dL.

289 If the participant receives a Control-IQ Low Alert, a message appears on the user interface that is
290 accompanied by vibration followed by vibrations and/or sound if not acknowledged by the user in 5
291 minutes. This alert remains on the screen until acknowledged by the participant. The user is prompted
292 to test blood glucose and treat with carbohydrate.

293 Participants on GLP-1 receptor agonists and DPP-4 inhibitors will be reminded to carefully monitor post
294 prandial blood sugars, as use of GLP-1 receptor agonists can have lower blood glucose levels after meals.

295 The participant and companion if available will be instructed that if severe hypoglycemia occurs, the
296 study pump's insulin delivery should be suspended and glucagon administration if the participant is
297 unable to consume carbohydrate.

298 Participants will be required to have a home glucagon emergency kit. Participants who currently do not
299 have one will be given a prescription for the glucagon emergency kit.

300 **3.1.3 Training on Management of Hyperglycemia**

301 The t:slim X2 with Control-IQ system will issue a predictive hyperglycemia alert (Control-IQ High Alert)
302 when the system has increased insulin delivery, but detects a CGM value above 200 mg/dL and does not
303 predict the value will decrease in the next 30 minutes. During the course of the study, participants will be
304 permitted to change the CGM high glucose threshold alert setting on their device or mobile app, but will
305 be instructed to choose a value no greater than 300 mg/dL.

306 If the participant receives a Control-IQ High Alert, a prompt appears on the user interface to check the
307 site for occlusion and test blood glucose.

308 If a participant's CGM reading is >300 mg/dL for more than 60 minutes or is ≥ 400 mg/dL at any point,
309 the participant will be instructed to take the following steps:

- 310 • Perform a blood glucose meter check.
- 311 • If the blood glucose is >300 mg/dL, check for blood ketones with the study ketone meter.
- 312 • If the ketone level is ≥ 0.6 mmol/L (or ≥ 2.5 mmol/L at any time), take correction insulin, change
313 insulin (pump) infusion site and contact study staff. Continue to monitor their glucose and blood
314 ketone levels until they return to normoglycemia and ketones are < 0.6 mmol/l.
 - 315 ◆ If ketones are <0.6 mmol/l, they will be advised to continue to monitor their glucose until it
316 returns to normoglycemia and to repeat the ketone measurement in 90 minutes if necessary
- 317 • If correction insulin is administered via insulin syringe, turn Control-IQ off for four hours and until
318 glucose level has returned to <180 mg/dL.

319

320 **Special Considerations for Participants Taking SGLT-2 inhibitors, GLP-1 Receptor Agonists, or**
321 **DPP-IV Inhibitors**

322 Participants taking any SGLT-2 inhibitor will be instructed to perform scheduled ketone checks at least
323 twice a day (morning and evening) during the first two weeks of study device use, and at least once a day
324 thereafter. If a participant taking an SGLT-2 inhibitor develop ketones > 0.6 on two successive occasions
325 during these 2 weeks (the first testing upon waking in a fasted state), they will be withdrawn from the
326 study.

327 For participants taking any SGLT-2 inhibitor, GLP-1 Receptor Agonist, or DPP-4 inhibitor, if a
328 participant's CGM reading is >250 mg/dL for more than 60 minutes or is ≥ 400 mg/dL at any point, the
329 participant will be instructed to take the following steps:

- 330 • Perform a blood glucose meter check.
- 331 • If the blood glucose is >250 mg/dL, check for blood ketones with the study ketone meter.
- 332 • If the ketone level is ≥ 0.6 mmol/L (or ≥ 2.5 mmol/L at any time), take correction insulin, change
333 insulin (pump) infusion site and contact study staff. Continue to monitor their glucose and blood
334 ketone levels until they return to normoglycemia and ketones are < 0.6 mmol/l.
 - 335 ◆ If ketones are <0.6 mmol/l, they will be advised to continue to monitor their glucose until it
336 returns to normoglycemia and to repeat the ketone measurement in 90 minutes if necessary
- 337 • If correction insulin is administered via insulin syringe, turn Control-IQ off for four hours and until
338 glucose level has returned to <180 mg/dL.

339

340 **3.1.4 Adjustments in Insulin Pump Settings**

341 Insulin and glucose data from the screening visit, as well as follow up visits, will be reviewed and the site
342 investigator may adjust insulin delivery profile settings as needed in accordance with their clinical
343 practice.

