8.2 Sample Size

818 The sample size of at least 30 completers of the trial was selected to have a reasonable number of hours of
819 use, with each subject completing approximately 3 months use of the study system with the removal of
820 the basal clipping feature, and not for assessing safety endpoints and is not based on statistical principles.

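### For a syringe correction given during hyperglycemia, 3.1.1 omits the glucose condition that 3.1.3 sets for restarting Control-IQ, and nothing links the two

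*Combined protocol and SAP*

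**What the plan says.** Section 3.1.1 makes closed loop the default and lists the exceptions: "The participant will be instructed to use the system in closed-loop mode except 1) when no calibrated" CGM sensor is available, or when insulin reaches the participant by a route other than the study pump. Its example of the second exception, and the rule that follows it, read "injection of subcutaneous insulin via syringe in the event of infusion site failure). If insulin is delivered" "by any means other than the study pump, participant will be instructed to turn off Control-IQ for" "approximately four hours". No glucose level is attached.

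Section 3.1.3 sets out what to do in prolonged or marked hyperglycemia: a meter check, a ketone check, and, if ketones are raised, correction insulin, a site change and a call to study staff. Its last step is "If correction insulin is administered via insulin syringe, turn Control-IQ off for four hours and until" "glucose level has returned to <180 mg/dL". The same step closes the separate part of 3.1.3 for participants on SGLT-2 inhibitors, GLP-1 receptor agonists or DPP-4 inhibitors.

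Section 3.1.1 also says that participants receive the Hypoglycemia and Hyperglycemia "Treatment Guidelines as part of the Study Participant Instruction Sheet". That sheet is not among the documents available for review.

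**The concern.** Both sections tell the participant when to go back to the investigational mode after injected insulin, and their triggers overlap. The example in 3.1.1, a syringe injection after infusion-site failure, is also a situation the 3.1.3 steps are meant to handle. In that overlap one section gives a time and the other gives a time plus a glucose level.

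The instruction matters because it decides whether the algorithm is running after an infusion-site problem. Section 1.3.1.4 names a poorly working infusion set and prolonged suspension of delivery as routes to hyperglycemia and ketonemia, and section 1.3.1.6 names over-delivery as a system risk. A participant, trainer or monitor should be able to tell from the protocol which condition ends the off-period. As written, someone who restarts at four hours with glucose at, say, 240 mg/dL has followed 3.1.1 and departed from 3.1.3.

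**Working it through.** The plan gives no figure to reproduce. The check is a comparison of the two instructions on trigger, time off and glucose condition.

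| | 3.1.1 | 3.1.3 (both parts) |
|---|---|---|
| Trigger | Any insulin not given by the study pump | Correction insulin by syringe within the hyperglycemia steps |
| Time off | About four hours | Four hours |
| Glucose condition | None | Below 180 mg/dL |

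**Step 1: where both apply.** A syringe correction within the 3.1.3 steps is also insulin not given by the pump, so it meets both triggers. Injected insulin outside those steps meets only 3.1.1, and there is no conflict.

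**Step 2: compare within the overlap.**

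- Before four hours: both keep Control-IQ off, apart from the small difference between about four and four hours.
- At four hours, glucose below 180 mg/dL: both allow restart.
- At four hours, glucose 180 mg/dL or above: the off-period in 3.1.1 has ended and its default is closed loop, while 3.1.3 keeps Control-IQ off.

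Only the third case separates them in substance.

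**Step 3: how far glucose must fall for the two to agree.** The 3.1.3 steps start at CGM above 300 mg/dL for more than 60 minutes (above 250 mg/dL in the adjunct-drug part), or at 400 mg/dL or more at any point in either part. To be below 180 mg/dL at four hours, glucose must have fallen from the starting threshold by more than:

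- 300 − 180 = 120 mg/dL (general part)
- 250 − 180 = 70 mg/dL (adjunct-drug part)
- 400 − 180 = 220 mg/dL (the any-point trigger)

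These differences show what agreement requires. They say nothing about frequency: the documents give neither the expected number of syringe corrections nor the share still at or above 180 mg/dL at four hours.

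**Step 4: look for a sentence that settles it.** Section 3.1.1 has no reference to 3.1.3 where it states the off-period. Section 3.1.3 does not say that it adds to or overrides 3.1.1. Section 5.1 says that the guidelines in 3.1.3 and 3.1.2 stay in effect during the challenges, which does not rank 3.1.3 against 3.1.1.

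**Step 5: look for an effect on the analysis.** Severe hypoglycemia and DKA are counted in all participants who start the Treatment Period and use the device, with no split by operating mode (8.4, 8.5.1). Section 8.5.3 tabulates time in each mode as it occurs. Section 8.2 says that the number of completers was chosen for hours of use without "the basal clipping feature, and not for assessing safety endpoints and is not based on statistical principles". None of these depends on which restart condition is followed.

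**The case against.** The strongest reply is that this is an ordinary general rule with a specific one. Section 3.1.3 keeps the four hours and adds a glucose condition for a narrower situation, so a careful reader would apply the stricter wording there. Both sections belong to the same training visit, and 3.1.1 itself says that participants are given the hyperglycemia guidelines. In addition, the one step in 3.1.3 that calls for correction insulin also tells the participant to contact study staff and to keep checking glucose and ketones, so the participant is not left alone with two sentences.

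Most of this stands, and it limits the point. It does not remove it. The general-and-specific reading is reasonable, but the protocol never states it. Receiving the guidelines means that a participant may be given both instructions, not that the difference is settled. Contact with staff helps only if staff know which condition applies.

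A reader might infer more than the documents support:

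- **That sites will train opposite behaviour.** The rules agree except at 180 mg/dL or above at four hours, and how sites train is not described.
- **That only 3.1.3 applies during the meal and exercise challenges.** Section 5.1 names 3.1.3 and 3.1.2, and it does not suspend 3.1.1.
- **That the primary safety results are distorted.** Relatedness turns on whether the device functioned as intended (6.2.3, 6.2.4) and is adjudicated by the Medical Monitor (6.5). It does not turn on which restart sentence was followed.

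**Conclusion.** The inconsistency is real and narrow. For a syringe correction given within the 3.1.3 hyperglycemia steps, the protocol states two different conditions for ending the Control-IQ off-period, and they lead to different actions when glucose is still 180 mg/dL or above at four hours. Elsewhere they agree, or only 3.1.1 applies.

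Its size cannot be given as a number of events, and any effect on safety events is possible but unquantified. No sample size, error rate or planned analysis changes. It is worth correcting because it is a participant safety instruction and the correction is cheap.

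The conclusion assumes that the Study Participant Instruction Sheet does not already settle the matter. If it does, the protocol text still needs to be aligned with it. No view is taken here on which restart condition is clinically right.

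**What to change.** Reconcile 3.1.1 with both parts of 3.1.3 so that one restart condition covers a syringe correction given for hyperglycemia, and add a cross-reference to 3.1.3 where 3.1.1 states the off-period. Check that the Study Participant Instruction Sheet carries the same condition. The sponsor's medical team decides which condition that is.

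The cost is a few words in two sections and a check of the sheet. No extra recording by sites is needed: electronic device files are already primary source documentation (9.1), and time in each operating mode is already to be tabulated (8.5.3), so the device data must capture when Control-IQ was off and on.

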4.3 Participant Access to Study Device at Study Closure

419

Participant will return all investigational study devices and supplies (insulin pump, CGM and related supplies) at study closure. Participant may keep the study ketone meter and study glucometer if these devices are not marked for investigational use only.

422 Chapter 5: Testing Procedures and Questionnaires

423 5.1 Meal and Exercise Challenges

424 Participants will complete 3 meal and 3 exercise challenges with the study device.

425 A minimum of 48 hours will occur between all challenges for each participant. Challenges may be
426 performed in any order.

427 Participants will be instructed to communicate with study staff within one day prior to each challenge to
428 review procedures and to have a contact with study staff after the completion of each challenge.

429 Hyperglycemia and Hypoglycemia treatment guidelines (sections 3.1.3 and 3.1.2) remain in effect for the
430 challenges, and will be reviewed with participants prior to each challenge.

431 Participants will be reminded they must have a care partner, trained in these hypoglycemia and
432 hyperglycemia treatment guidelines, present during the challenges and overnight until 6 AM the next day.

433 Site staff will directly contact the participant if they do not receive a follow up contact from participants
434 when 24 hours have passed since the time of completion of the planned challenge.

435 5.1.1 Meal Challenges

436 The same meal should be used for each of the three meal challenges—either lunch or dinner (participant
437 choice).

438 During study device use, the three meal challenges will consist of:

- 439 • No bolus for the meal
- 440 • 50% bolus - calculate the bolus dose using the bolus calculator, and deliver half the
441 recommended dose of insulin.
- 442 • Full bolus for the meal based on calculated bolus dose using the bolus calculator.

443 For each meal challenge, participants will:

- 444 1. Be in a fasting state for two hours prior to consuming the meal and the last manual insulin bolus
445 more than two hours prior to the meal.
- 446 2. Only begin the meal challenge if CGM glucose is between 70 mg/dL and 200 mg/dL. *Subjects
447 with hyperglycemia > 200mg/dL will reschedule their challenge for another time. If < 70 mg/dL,
448 carbohydrate treatment can be given, after which the meal challenge can continue.*
- 449 3. Consume at least 50 grams carbohydrate for the meal. *Each participant will use the same meal

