- 574 • a hypoglycemic event occurred meeting the following definition of severe hypoglycemia: the event
575 required assistance of another person due to altered consciousness, and required another person to
576 actively administer carbohydrate, glucagon, or other resuscitative actions. This means that the
577 participant was impaired cognitively to the point that he/she was unable to treat himself/herself, was
578 unable to verbalize his/ her needs, was incoherent, disoriented, and/or combative, or experienced
579 seizure or loss of consciousness. These episodes may be associated with sufficient neuroglycopenia to
580 induce seizure or loss of consciousness. If glucose measurements are not available during such an
581 event, neurological recovery attributable to the restoration of glucose to normal is considered
582 sufficient evidence that the event was induced by a low glucose concentration.
- 583 • evaluation or treatment was obtained at a health care provider facility for an acute event involving
584 hypoglycemia, or the participant contacted the site and received guidance following the occurrence of
585 an acute event involving hypoglycemia

586 When a severe hypoglycemia event occurs (as defined above), an Adverse Event Form should be
587 completed. Severe hypoglycemia events should be considered to be serious adverse events with respect to
588 reporting requirements. When a severe hypoglycemia event occurs during use of a study device, it
589 generally will be considered to be unrelated to the device (per section 6.2.5) if the device functioned as
590 intended and there does not appear to be a flaw in how the device is intended to function.

591 **6.2.4 Hyperglycemic/Ketotic Events**

592 Hyperglycemia is only reportable as an adverse event when one of the following criteria is met:

- 593 • the event involved DKA, as defined by the Diabetes Control and Complications Trial (DCCT) and
594 described below
- 595 • evaluation or treatment was obtained at a health care provider facility for an acute event involving
596 hyperglycemia or ketosis, or the participant contacted the site and received guidance on how to
597 manage the hyperglycemia/ketosis
- 598 • blood ketone level ≥ 0.6 mmol/L, even if there was no communication with a health care provider at
599 the time of the event

600 Hyperglycemic events are classified as DKA if the following are present:

- 601 • Symptoms such as polyuria, polydipsia, nausea, or vomiting;

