- 602 • Serum ketones > 1.5 mmol/L or large/moderate urine ketones;
- 603 • Either arterial blood pH < 7.30 or venous pH < 7.24 or serum bicarbonate (or CO₂) < 15 ; and
- 604 • Treatment provided in a health care facility

605 When a hyperglycemia/ketotic event qualifies as an SAE as defined in section 6.2.1, an Adverse Event
606 Form should be completed. Events meeting DKA criteria should be considered to be serious adverse
607 events with respect to reporting requirements. Hyperglycemia events not meeting criteria for DKA

608 generally will not be considered as serious adverse events unless one of the SAE criteria in section 6.2.1
609 is met.

610 DKA can occur at “euglycemic” glucose levels less than 250 mg/dL, and may occur more commonly in
611 individuals taking adjuvant medications for glucose control such as SGLT-2 inhibitors. This should be
612 reported as a DKA event if it occurs.

613 When a hyperglycemia/DKA event occurs during use of a study device, it generally will be considered to
614 be unrelated to the device (per section 6.2.5) if the device functioned as intended and there does not
615 appear to be a flaw in how the device is intended to function.

616 **6.2.5 Relationship of Adverse Event to Study Investigational Device**

617 The study investigator will assess the relationship of any adverse event to the study device or study drug.
618 The Medical Monitor also will make this assessment, which may or may not agree with that of the study
619 investigator. Reporting requirements will be based on the Medical Monitor’s assessment.

620 To ensure consistency of adverse event causality assessments, investigators should apply the following
621 general guidelines when determining whether an adverse event is related to a study device or study drug:

622 **Unrelated:** The AE is clearly not related to a study drug/device and a likely alternative etiology exists
623 such as an underlying disease, environmental or toxic factors or other therapy.

624 **Unlikely Related:** The AE does not follow a reasonable temporal sequence during or after use of study
625 drug/device and a more likely alternative etiology exists such as an underlying disease, environmental or
626 toxic factors, or other therapy.

627 **Possibly Related:** The AE occurred in a reasonable time during or after use of study drug/device; but
628 could be related to another factor such as an underlying disease, environmental or toxic factors, or other

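### After week 2, section 3.1.3 states no ketone-triggered action for an SGLT-2 inhibitor user's scheduled reading from 0.6 to below 2.5 mmol/L unless the glucose-triggered steps are active

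*Combined protocol and SAP*

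**What the plan says.** Section 7.3 lets participants stay on an SGLT-2 inhibitor if the dose has been stable for 3 months, and refers to section 3.1.3 for their extra monitoring. Section 3.1.3 then sets three rules.

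- **Schedule.** "Participants taking any SGLT-2 inhibitor will be instructed to perform scheduled ketone checks at least" twice a day in the first two weeks and at least once a day after that. No glucose condition applies.
- **Withdrawal.** Users who "develop ketones > 0.6 on two successive occasions" within those two weeks leave the study.
- **Action steps.** These start when CGM is above 250 mg/dL for more than 60 minutes, or at 400 mg/dL or more at any point. After a meter check comes "If the blood glucose is >250 mg/dL, check for blood ketones with the study ketone meter", and then "If the ketone level is ≥ 0.6 mmol/L (or ≥ 2.5 mmol/L at any time), take correction insulin, change" the infusion site and contact study staff.

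In section 6.2.4 one of the four DKA criteria is "Serum ketones > 1.5 mmol/L or large/moderate urine ketones"; the others are symptoms, acidosis and treatment in a health care facility. The same section says DKA can occur at "glucose levels less than 250 mg/dL, and may occur more commonly in" people taking drugs such as SGLT-2 inhibitors, and that such an event must be reported as DKA.

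**The concern.** A scheduled check that ignores glucose is there to find ketosis that a glucose alarm would miss. Section 3.1.3 requires the check but, after week 2, ties its response to glucose for every reading below 2.5 mmol/L. That stand-alone level is the same one given to participants who take none of these drugs, and it lies above the ketone component of the protocol's own DKA definition.

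Take an SGLT-2 user in week 5 with ketones of 2.0 mmol/L and glucose of 200 mg/dL. Section 3.1.3 gives this person nothing to do in response to the ketone value. Same-day help depends on the participant deciding that the reading deserves a call, and the next required check may be about 24 hours away. DKA is a primary safety endpoint (section 8.3), and three hyperglycemic or ketotic events qualifying as serious suspend closed-loop use across the study (section 6.6.2).

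**Working it through.** The plan states no figure on this point, so the check is a trace of the rules, followed by simple counts.

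**Rules by period and ketone level, for an SGLT-2 user.** Steps active means CGM above 250 mg/dL for more than 60 minutes or at least 400 mg/dL, with meter glucose above 250 mg/dL.

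| Period | Glucose-triggered steps | 0.6 to 1.5 mmol/L | above 1.5 to below 2.5 mmol/L | 2.5 mmol/L or more |
|---|---|---|---|---|
| Weeks 1-2 | not active | one reading: none stated; two successive above 0.6: withdrawal | same | correction insulin, site change, call staff |
| Weeks 1-2 | active | correction insulin, site change, call staff; withdrawal rule also applies | same | same |
| After week 2 | not active | **none stated** | **none stated** | correction insulin, site change, call staff |
| After week 2 | active | correction insulin, site change, call staff | same | same |

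The single-reading gap in weeks 1-2 is minor, because checks are at least morning and evening. The not-active rows are not confined to glucose at or below 250 mg/dL. A reading of 2.0 mmol/L when CGM has been at 270 mg/dL for 20 minutes also falls there, because the 60-minute condition is not yet met.

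**Could the 0.6 level apply to any reading?** If it did, the 2.5 mmol/L parenthesis would be redundant, since every reading of 2.5 is also above 0.6. If instead the parenthesis were confined to the glucose-triggered steps, the gap would be wider.

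**Other places that could supply an action.**

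- Section 3.1.1: the SGLT-2 hold is triggered by fever, gastrointestinal illness, dehydration, poor intake, fasting or significant illness, not by a ketone value.
- Section 3.1.1: advice to call staff about health-related issues gives no ketone level.
- Section 3.1.1: training on infusion-set failure includes a ketone check but no ketone threshold.
- Section 4.1.4: ketone measurement is described only as a way to evaluate prolonged hyperglycemia.
- Section 6.2.4: "blood ketone level ≥ 0.6 mmol/L, even if there was no communication with a health care provider at" the time makes the reading reportable as an adverse event. This is a recording rule.

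None sets a same-day action triggered by ketones.

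**Exposure.** The final visit window is days 91-98 (section 3.2).

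- Days after week 2: 91 − 14 = 77, and 77/91 = 85%; or 98 − 14 = 84, and 84/98 = 86%.
- At one check a day or more, that is at least 77 to 84 scheduled checks per SGLT-2 user who completes. These count opportunities, not events.

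**Visit-table contacts.** Weeks 3, 6, 9 and 13 fall nominally on days 21, 42, 63 and 91, so the gaps are 42 − 21 = 21, 63 − 42 = 21 and 91 − 63 = 28 days.

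**Challenge contacts.** Section 5.1 requires staff contact before and after each of 3 + 3 = 6 challenges, so up to 6 × 2 = 12 further contacts. The challenges must be at least 48 hours apart, but their dates are otherwise not fixed.

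**The case against.** The strongest reply is that participants are better covered than section 3.1.3 alone suggests. Much of it is fair.

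- **Contacts.** A reader might infer from the visit table that a reading could go unseen for the full interval between visits. The documents do not support this. The challenge contacts come on top of the table, the protocol summary has adverse events assessed at all visits and contacts, and further contacts are allowed as needed. The true maximum gap is unknown. What stands is that none of these contacts is triggered by a ketone reading.
- **Training.** Participants learn to suspect infusion-set failure, to check ketones and to call about health issues, and the Control-IQ High Alert can prompt a site check above 200 mg/dL. These make a sensible call more likely, but leave the decision to the participant.
- **Instruction sheet.** A reader might infer that participants are given no instruction at all for these readings. That cannot be shown, because the sheet was not available and the treatment guidelines are only part of it. Section 5.1 does identify those guidelines with the text examined here: "Hyperglycemia and Hypoglycemia treatment guidelines (sections 3.1.3 and 3.1.2) remain in effect for the" challenges. What is shown is a gap in section 3.1.3.
- **The 1.5 mmol/L level.** Section 6.2.4 uses it to classify events, not to prompt action. A reader might infer that a reading above 1.5 mmol/L is DKA left untreated. It is not: three other criteria must also be met. The level is a convenient anchor already in the protocol, and the sponsor may prefer a lower one.
- **Risk among those who continue.** A stable dose for 3 months and withdrawal for repeated early readings both lower the risk. This limits the urgency without supplying the missing response.

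**Conclusion.** The gap is real on the text and narrow. It concerns SGLT-2 inhibitor users, mainly after week 2, with scheduled readings from 0.6 to below 2.5 mmol/L while the glucose-triggered steps are not active. The part that matters most is above 1.5 mmol/L. It spans about 85% of the treatment period and at least 77 checks per SGLT-2 user who completes.

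No event rate can be attached to it, because the number of SGLT-2 users is not given and could be zero. The conclusion assumes that the action steps are read as laid out, under their glucose trigger, and that the instruction sheet adds nothing beyond section 3.1.3. If the sheet does add a response, only the protocol wording needs to catch up. This is a cheap improvement.

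**What to change.** In the SGLT-2 part of section 3.1.3 and in the participant instruction sheet:

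- Keep the action at 2.5 mmol/L or more and the weeks 1-2 withdrawal rule as they are.
- Add that any scheduled reading above 1.5 and below 2.5 mmol/L requires same-day contact with study staff and a repeat ketone check, with insulin and carbohydrate given under staff guidance. The sponsor may set a lower starting level.
- Apply this at any point in the study and at any glucose when the glucose-triggered steps do not already apply. A limit of 250 mg/dL or less would miss readings taken during the first 60 minutes above 250 mg/dL.

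Staff guidance matters because correction insulin at near-normal glucose should not be left to the participant alone. Unless a lower level is chosen, readings of 0.6 to 1.5 mmol/L outside the glucose-triggered steps stay under adverse event reporting, plus the withdrawal rule in weeks 1-2. If the instruction sheet already has such a rule, copy it into section 3.1.3. The cost is a few lines of wording and a few extra staff contacts.
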